6.2.1. Preparation and Dispensing

See the IPM for instructions on how to prepare the study intervention for administration. Study intervention should be prepared and dispensed by an appropriately qualified and experienced member of the study staff (eg, physician, nurse, physician's assistant, nurse practitioner, pharmacy assistant/technician, or pharmacist) as allowed by local, state, and institutional guidance. A second staff member will verify the preparation and dispensing.

6.3. Assignment to Study Intervention

Allocation (randomization) of participants to vaccine groups, and/or the assignment of study intervention to be dispensed to the participant, as applicable to the substudy, will proceed through the use of an IRT system.

Study intervention will be dispensed at the study visits summarized in the substudy SoA.

The study-specific IRT reference manual and IPM will provide the contact information and further details on the use of the IRT system.

For further details for Substudy A, refer to [Section 10.7.6.1](#).

For further details for Substudy B, refer to [Section 10.8.6.1](#).

6.4. Blinding

Blinding arrangements for participants, site personnel, and the sponsor for Substudy A are detailed in [Section 10.7.6.2](#).

Blinding arrangements for participants, site personnel, and the sponsor for Substudy B are detailed in [Section 10.8.6.2](#). Substudy B is an open-label study.

6.5. Study Intervention Compliance

When participants are dosed at the site, they will receive study intervention directly from the investigator or designee, under medical supervision. The date and time as well as the anatomical location of each dose administered in the clinic will be recorded in the source documents and recorded in the CRF. The dose of the study intervention and study participant identification will be confirmed at the time of dosing by a member of the study site staff other than the person administering the study intervention.

The site will complete the required dosage Preparation Record located in the IPM. The use of the Preparation Record is preferred, but it does not preclude the use of an existing appropriate clinical site documentation system. The existing clinical site's documentation system should capture all pertinent/required information on the preparation and administration of the dose. This may be used in place of the Preparation Record after approval from the sponsor and/or designee.

6.6. Dose Modification

Not applicable.

6.7. Continued Access to Study Intervention After the End of the Study

No study intervention will be provided to participants at the end of their study participation.

6.8. Treatment of Overdose

For this study, any dose of study intervention greater than 1 dose of study intervention within a 24-hour time period will be considered an overdose.

There is no specific treatment for an overdose.

In the event of an overdose, the investigator should:

1. Contact the study medical monitor within 24 hours.
2. Closely monitor the participant for any AEs/SAEs as medically appropriate and follow up until resolution, stabilization, the event is otherwise explained, or the participant is lost to follow-up (as defined in [Section 7.3](#)).
3. Document the quantity of the excess dose as well as the duration of the overdose in the CRF.
4. Overdose is reportable to Pfizer Safety only when associated with an SAE.

6.9. Prior and Concomitant Therapy

6.9.1. Prohibited Concomitant Vaccinations and Treatments

For Substudy A, refer to [Section 10.7.6.7.1](#).

For Substudy B, refer to [Section 10.8.6.7.1](#).

6.9.2. Permitted Concomitant Vaccinations and Treatments

For Substudy A, refer to [Section 10.7.6.7.2](#).

For Substudy B, refer to [Section 10.8.6.7.2](#).

7. DISCONTINUATION OF STUDY INTERVENTION AND PARTICIPANT DISCONTINUATION/WITHDRAWAL

7.1. Discontinuation of Study Intervention

Substudy A is a single-dose substudy; therefore, this section is not applicable to that substudy.

Substudy B: It may be necessary for a participant to permanently discontinue study intervention. Reasons for permanent discontinuation of study intervention include the following: AEs, participant request, investigator request, and protocol deviation (including no longer meeting all the inclusion criteria or meeting 1 or more exclusion criteria).

Discontinuation of study intervention does not represent withdrawal from the study. If study intervention is permanently discontinued, the participant should remain in the study to be

evaluated for safety and, where applicable, immunogenicity. See the [SoA](#) for data to be collected at the time of discontinuation of study intervention and follow-up for any further evaluations that need to be completed.

In the event of discontinuation of study intervention, it must be documented on the appropriate CRF/in the medical records whether the participant is discontinuing further receipt of study intervention or also from study procedures, further study follow-up, and/or future collection of additional information.

7.2. Participant Discontinuation/Withdrawal From the Study

A participant may withdraw from the study at any time at their own request. Reasons for discontinuation from the study include the following:

- Refused further study procedures;
- Lost to follow-up;
- Death;
- Study terminated by sponsor;
- AEs;
- Participant request;
- Investigator request;
- Select protocol deviations (Note: Receipt of an RSV vaccine outside of the study will result in study withdrawal).

If a participant withdraws from the study, they may request destruction of any remaining samples taken and not tested, and the investigator must document any such requests in the site study records and notify the sponsor accordingly.

If the participant withdraws from the study and also withdraws consent (see [Section 7.2.1](#)) for disclosure of future information, no further evaluations will be performed and no additional data will be collected. The sponsor may retain and continue to use any data collected before such withdrawal of consent.

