8.4.1. Time Period and Frequency for Collecting AE and SAE Information

The time period for actively eliciting and collecting AEs and SAEs (“active collection period”) for each participant begins from the time the participant provides informed consent, which is obtained before the participant’s participation in the study (ie, before undergoing any study-related procedure and/or receiving study intervention), through and including approximately 1 month following the last administration of the study intervention, and AESIs, NDCMCs, and SAEs will be collected from informed consent throughout study participation. In addition, AEs occurring up to 48 hours after blood draws that are related to study procedures will be collected.

Follow-up by the investigator continues throughout the active collection period and until the AE or SAE or its sequelae resolve or stabilize at a level acceptable to the investigator.

When a clinically important AE remains ongoing at the end of the active collection period, follow-up by the investigator continues until the AE or SAE or its sequelae resolve or stabilize at a level acceptable to the investigator and Pfizer concurs with that assessment.

For participants who are screen failures, the active collection period ends when screen failure status is determined.

If the participant withdraws from the study and also withdraws consent for the collection of future information, the active collection period ends when consent is withdrawn.

If a participant permanently discontinues or temporarily discontinues study intervention, or discontinues from the study, because of an AE or SAE, the AE or SAE must be recorded on the CRF and the SAE reported via PSSA or using the Vaccine SAE Report Form.

Investigators are not obligated to actively seek information on AEs or SAEs after the participant has concluded study participation. However, if the investigator learns of any SAE, including a death, at any time after a participant has concluded study participation, and they consider the event to be reasonably related to the study intervention, the investigator must promptly report the SAE to Pfizer via PSSA or using the Vaccine SAE Report Form.

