8.4.8. Adverse Events of Special Interest

The following events are considered AESIs in Substudy A and Substudy B:

- Diagnosis of Guillain-Barre syndrome
- Diagnosis of acute polyneuropathy without an underlying etiology
- Diagnosis of atrial fibrillation
- Preterm delivery (delivery at <37 0/7 weeks' gestation)
- Diagnosis of a hypertensive disorder of pregnancy

Details of the AESIs listed above are further defined in the investigator site file.

All AESIs must be reported as an AE or SAE following the procedures described in Sections [8.4.1](#) through [8.4.4](#) from the time the participant provides informed consent through the end of study participation. An AESI is to be recorded as an AE or SAE on the CRF. In addition, an AESI that is also an SAE must be reported via PSSA or using the Vaccine SAE Report Form.

AESIs are examined as part of routine safety data review procedures throughout the clinical trial and as part of signal detection processes. Should an aggregate analysis indicate that these prespecified events occur more frequently than expected, eg, based on epidemiological data, literature, or other data, then this will be submitted and reported in accordance with Pfizer's safety reporting requirements. Aggregate analyses of safety data will be performed on a regular basis per internal SOPs.

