10.7.6.7.1. Prohibited Concomitant Vaccinations and Treatments for Substudy A

Receipt of the following vaccines and medications during the time periods listed below may exclude a participant from the per-protocol analysis from that point onward; however, it is anticipated that the participant would not be withdrawn from the study (unless documented as per [Section 7.2](#)). Medications should not be withheld if required for a participant's medical care.

- Receipt of any nonstudy RSV vaccine at any time prior to or during study participation.
- Investigational vaccines, drugs, or medical devices are prohibited during the course of the study.

Note: COVID-19 vaccines authorized for temporary or emergency use will not be prohibited during the course of this study if administered more than 14 days prior to study intervention administration or at least 14 days after study intervention administration.

- Receipt of blood/plasma products or immunoglobulin (IVIG, SCIG) prior to the final blood draw.

Note: Monoclonal antibodies with targeted mechanisms of action used in the management of chronic illnesses (eg, migraine headaches, osteoporosis) are permitted, provided they do not meet exclusion criterion 7.

- Nonstudy vaccines may not be given concomitantly with the study intervention or within 14 days after study intervention administration, except if medically necessary (eg, during an outbreak or pandemic situation).
- Receipt of chronic systemic treatment with known immunosuppressant medications within 60 days before study intervention administration through conclusion of the study.

- Receipt of systemic corticosteroids (≥ 20 mg/day of prednisone or equivalent) for ≥ 14 days is prohibited from 28 days prior to study intervention administration through Day 28 after administration of the study intervention.

Note: Inhaled/nebulized, intra-articular, intrabursal, or topical (skin or eyes) corticosteroids are permitted.

- Prophylactic antipyretics and other pain medication to prevent symptoms associated with study intervention administration are not permitted before administration of study intervention.

Note: If a participant is taking a medication for another condition, even if it may have antipyretic or pain-relieving properties, it should not be withheld prior to study vaccination.

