### 2.2.1.3. Substudy A Primary Safety Estimands

#### 2.2.1.3.1. Reactogenicity Estimands

Reactogenicity estimands have the following 5 attributes:

- **Treatment condition:** RSVpreF or placebo received on Day 1 in Substudy A.
- **Population:** Participants as defined by the study inclusion/exclusion criteria for Substudy A.
- **Variables:** Each item included in the e-diary from Days 1 through 7 after vaccination (refer to [Section 3.1.3.1](#) and [Section 3.1.3.2](#)).
- **Intercurrent events:** All data collected after the intercurrent events will be included.
- **Population-level summary:** The rates of reporting each reactogenicity item in each treatment condition.

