##### 6.1.4.1. Main Analysis

- Estimand strategy: Treatment policy ([Section 2.2.1.3.2](#), [Section 2.2.1.3.3](#), [Section 2.2.1.3.4](#), [Section 2.2.1.4.2](#), [Section 2.2.1.4.3](#), and [Section 2.2.1.4.4](#)).
- Intercurrent events and missing data: All data collected are included.
- Analysis set: Safety population ([Section 4](#)).
- Analysis timing: At primary analyses (when all primary endpoint data are available).
- Analysis methodology: 95% CIs of the proportion of participants reporting those events will use the Clopper-Pearson method ([Section 5.2.1](#)).
- Descriptive statistics, including the proportion (%), the numerator (n) and the denominator (N) used in the proportion calculation, and the 95% CI for percentage using the Clopper-Pearson method, will be presented for each vaccine group for each analysis interval ([Section 5.2.1](#)).
- Bar charts with the proportions of participants for each variable within the specified interval will be plotted for each group. The bars may be divided into relatedness categories to highlight the proportions of participants with related events.
- The main analysis would be based on AEs excluding the reactogenicity events that were reported in the AE CRF (except for SAEs) ([Section 3.1.3.3](#)).

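### Protocol 7.2 requires study withdrawal after an outside RSV vaccine and does not say that safety follow-up continues, although the SAP analyses safety by treatment policy

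*Protocol*

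**What the plan says.** **The withdrawal rule.** Protocol 7.2 lists reasons for leaving the study. Under selected protocol deviations it notes that "Receipt of an RSV vaccine outside of the study will result in study withdrawal". The note applies to both substudies.

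**Other prohibited treatments.** Protocol 10.7.6.7.1 (Substudy A), matched by 10.8.6.7.1 (Substudy B), says that after a prohibited vaccine or medicine "it is anticipated that the participant would not be withdrawn from the study", with an exception for what Section 7.2 provides. A nonstudy RSV vaccine is the first item on both lists.

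**The collection period.** Protocol 8.4.1 says that "AESIs, NDCMCs, and SAEs will be collected from informed consent throughout study participation". For AESIs, 8.4.8 sets the period "from the time the participant provides informed consent through the end of study participation". After that, "Investigators are not obligated to actively seek information on AEs or SAEs after the participant has concluded study participation" (8.4.1), although a related SAE that the investigator learns of must still be reported.

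**The explicit stop.** Protocol 8.4.1 describes one case: when a participant "withdraws from the study and also withdraws consent for the collection of future information, the active collection period ends when consent is withdrawn". Section 7.2 puts the same double condition on ending data collection.

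**The analysis.** SAP 6.1.4.1, for AEs, SAEs and NDCMCs, specifies "Estimand strategy: Treatment policy". SAP 2.2.1.3.1 says "All data collected after the intercurrent events will be included". SAP 2.2.1.4.1 says the same for Substudy B, and the AE, SAE and NDCMC estimands in both substudies inherit it. The summaries are proportions of the safety population with Clopper-Pearson intervals.

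**The concern.** A treatment-policy analysis needs data after the intercurrent event. Here the protocol turns one foreseeable event, vaccination elsewhere, into an exit from the study, while its rules for collecting late safety data are written in terms of being in the study. A site could reasonably stop contacting such a participant, or reasonably continue. The text does not settle which.

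Two features make this worth resolving. First, a withdrawn participant stays in the denominator. With no censoring or exposure adjustment, the unobserved months count as event-free unless an event was already recorded.

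Second, the loss would not fall evenly. Protocol 2.1 reports US approval of RSVpreF from age 60 and says no RSV vaccine is licensed for younger adults. About half of Substudy B is aged 60 or over. The outside product could also be RSVpreF itself, for which Protocol 2.3.1 names Guillain-Barre syndrome as a potential risk, so these participants' later safety data are of interest.

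**Working it through.** **Step 1. Does any section keep these participants under follow-up?**

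| Protocol section | Who it covers | Status | Safety follow-up |
|---|---|---|---|
| 7.1 | Substudy B, study intervention stopped | Remains in study | Continues |
| 7.2.1 | Asks to stop doses or active participation | Remains in study | Continues unless consent to contact is withdrawn |
| 7.2 and 8.4.1 | Withdraws and also withdraws consent | Out of study | Ends |
| 7.2 note | Received an outside RSV vaccine, consent intact | Withdrawn by rule | Not stated |

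Wherever follow-up is promised, it comes with remaining in the study, which the note rules out. Wherever collection is explicitly ended, consent has been withdrawn, which the note does not require. The fourth row is a gap.

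**Step 2. Direction of the effect.** The reported rate is x/N, where N is the number in the safety population and x the number with a recorded event. Stopping collection leaves N unchanged and can only remove participants from x. Hence x'/N ≤ x/N, and the Clopper-Pearson limits fall with it. This holds within each group. For a between-arm difference in Substudy A, the direction would depend on which arm lost more follow-up.

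**Step 3. Size.** The plan gives no figure to reproduce and no rate of outside vaccination, so uptake is assumed.

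Inputs: about 100 Substudy B participants aged 60 or over and about 7 months of participation (Protocol 10.8.4.1). Assumptions: 2% to 10% uptake, spread evenly over the 7 months, and collection stopping at once.

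- Planned follow-up: 100 × 7/12 = 58.3 person-years.
- Mean loss per withdrawn participant: 7/2 = 3.5 months.
- At 2%: 2 × 3.5/12 = 0.6 person-years; 0.6/58.3 = 1%.
- At 10%: 10 × 3.5/12 = 2.9 person-years; 2.9/58.3 = 5%.
- Over all of Substudy B: 200 × 7/12 = 116.7 person-years, so the loss is 0.5% to 2.5%.

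For uncommon events arising at a steady rate, the reported proportion would be understated by roughly the same relative amount.

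**Step 4. Wider assumptions.** Take 1% to 20% withdrawn at month 2 to month 4 of a 6-month follow-up, so 100 × 6 = 600 person-months.

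- Smallest loss: 100 × 0.01 × (6 − 4) = 2 person-months, or 0.3%.
- Largest loss: 100 × 0.20 × (6 − 2) = 80 person-months, or 13%.

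The same percentages would apply to the 675 × 2/3 = 450 RSVpreF recipients in Substudy A, but with no RSV vaccine licensed for their age group the low end is the relevant one.

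**Step 5. What is not touched.** The noninferiority analysis is unaffected by this gap. Its estimands are hypothetical and already exclude data after a prohibited vaccine (SAP 2.2.1.1). Sample size, power and alpha do not change.

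**The case against.** Four stronger readings are tempting, and the documents do not support them.

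- **That withdrawal under the note ends safety collection.** No section says so. The explicit stop requires withdrawn consent as well, and later related SAEs remain reportable. What stands is that continued follow-up is not stated either, and unrelated SAEs, NDCMCs and nonserious AESIs lack even that backstop.
- **That the safety estimand cannot be computed.** It can. The SAP uses whatever is collected, lists no specific safety intercurrent events, and tabulates withdrawals with reasons. The problem is truncated follow-up. AESIs have no estimand of their own; SAP 6.1.4.2 treats them as supplementary.
- **That the prohibited-treatment sections contradict Section 7.2.** They defer to it by cross-reference, so the exception is deliberate.
- **That the loss is material.** Planned receipt of an RSV vaccine is an exclusion criterion, and everyone in open-label Substudy B is due to receive RSVpreF, so uptake may be near or below the low end. Substudy B is single-arm and descriptive. Several windows also close early: under SAP 3.5.2, Guillain-Barre syndrome and acute polyneuropathy are counted as Tier 1 events to Day 43 after the last vaccination and atrial fibrillation to the 1-month visit, and general AEs stop 1 month after the last dose. Late withdrawal therefore mainly touches the study-long SAE, NDCMC and AESI summaries.

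The last argument limits the size of the problem. It does not close the gap in Step 1.

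**Conclusion.** The point holds as a gap between the withdrawal rule and the safety analysis. The protocol mandates withdrawal after an outside RSV vaccine, ties late safety collection to participation, and is silent on follow-up of these participants when consent is intact. Data that the treatment-policy analysis would use may therefore not be collected, and within a group the resulting error can only run towards lower reported rates.

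The likely size is small: 1% to 5% of person-time in Substudy B participants aged 60 or over. That rests on assumed uptake of 2% to 10%, even timing, and sites reading withdrawal as the end of collection. If sites continue contact, the loss is nil. The change is worth making because it is cheap and removes an avoidable source of under-ascertainment; no primary conclusion depends on it.

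**What to change.** Replace the note in Protocol 7.2 with wording to this effect: *Receipt of an RSV vaccine outside the study excludes later samples from the evaluable immunogenicity analysis. Unless consent is withdrawn, the participant stays in the study for all remaining protocol-specified safety collection: reactogenicity and AEs still within their windows, and SAEs, AESIs and NDCMCs to the final safety contact.*

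Align Protocol 7.2.1, 8.4.1, 8.4.8, 10.7.6.7.1 and 10.8.6.7.1 with it. The text should cover nonserious AEs and reactogenicity as well as the long-term events, because the SAP analyses those by treatment policy too. All dosing and eligibility rules stay as they are. If the sponsor already intends to follow these participants, a sentence saying so in 7.2 and 8.4.1 would be enough.

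**Cost.** One amended note, consistency edits in five sections, and a few contacts already in the schedules of activities; the final one may be by telephone. No new data field is needed, since nonstudy vaccinations are already recorded to the last visit. The immunogenicity exclusion matches the existing SAP strategy.

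**Downside.** A few later events will follow another vaccine. Treatment policy accepts that, and the recorded vaccination date makes those events visible.

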7.2.1. Withdrawal of Consent

Participants who request to discontinue receipt of study intervention (Substudy B) and/or active study participation (eg, biological sample collection) will remain in the study and must continue to be followed for protocol-specified safety follow-up procedures. The only exception to this is when a participant specifically withdraws consent for any further contact

with them or persons previously authorized by the participant to provide this information. Participants should notify the investigator in writing of the decision to withdraw consent from future follow-up, whenever possible. The withdrawal of consent should be explained in detail in the medical records by the investigator, as to whether the withdrawal is only from further receipt of study intervention or also from specified study procedures and/or postvaccination safety follow-up, and entered on the appropriate CRF page. In the event that vital status (whether the participant is alive or dead) is being measured, publicly available information should be used to determine vital status only as appropriately directed in accordance with local law.

